12.1.5 Summary of Injection Site Reactions (ISRs)

Target population	:	Safety Analysis Set
Analysis Items	:	Injection Site Reactions
Group	:	Placebo, Zilebesiran 300 mg, Zilebesiran 600 mg, Total zilebesiran, Overall Total
Content of analysis	:	
 The number of patients and the percentage, the number of signs and symptoms will be calculated for each group.
Definition	:	
 The denominator of proportions is the target population by groups.

12.1.6 Summary of Most Common ($\geq 5\%$) Treatment-emergent Adverse Events by SOC and PT

Target population	:	Safety Analysis Set
Analysis Items	:	Most common ($\geq 5\%$) Treatment-emergent Adverse Events
Group	:	Placebo, Zilebesiran 300 mg, Zilebesiran 600 mg, Total zilebesiran, Overall Total
Content of analysis	:	
 The number of patients with the event, and the percentage will be calculated by groups For symptoms (SOC, PT), the number of patients with symptoms and the percentage will be calculated by groups.
Definitions	:	
 The denominator of proportions is the target population by groups. Most common ($\geq 5\%$) Treatment-emergent Adverse Events are the events (PTs) with higher than or equal to 5% patients in any treatment group (Placebo, Zilebesiran 300 mg, Zilebesiran 600 mg).

12.2 Vital Signs, Weight, Height and BMI

12.2.1 Summary of Vital Sign Tests, Weight, Height and BMI by Visit

Target population	:	Safety Analysis Set
Analysis	:	Height, Weight, BMI, Body temperature, Heart Rate, Respiratory Rate

Items		
Group	:	Placebo, Zilebesiran 300 mg, zilebesiran 600 mg, Total zilebesiran, Overall Total
Time of analysis	:	Refer to section 2.8.1
Content of analysis	:	
 Calculate the summary statistics of measurement value, change from baseline and percent change from baseline for each quantitative item of the vital sign tests, Height, Weight, and BMI by groups and analysis time points.

12.2.2 Summary of Orthostatic Hypotension during 6-Month DB Period

Target population	:	Safety Analysis Set
Analysis Items	:	SBP, DBP
Group	:	Placebo, Zilebesiran 300 mg, Zilebesiran 600 mg, Total zilebesiran, Overall Total
Time of analysis	:	Refer to section 2.8.1
Content of analysis	:	
 The number of patients with orthostatic hypotension, the number of patients with assessment and the percentage of patients with orthostatic hypotension will be calculated for each group
Definition	:	
 Orthostatic hypotension is defined as SBP drop ≥ 20 mmHg or DBP ≥ 10 mmHg from sitting to standing.

12.2.3 Summary of Abnormalities in Vital Sign Tests

Target population	:	Safety Analysis Set
Analysis Items	:	Weight, Body temperature, Heart Rate, Respiratory Rate
Group	:	Placebo, Zilebesiran 300 mg, Zilebesiran 600 mg, Total zilebesiran, Overall Total
Content of analysis	:	
 The number and percentages of patients by groups, analysis items and category. Category is as follow: Weight: Increment $\geq 7\%$, Decrement $\geq 7\%$ Heart Rate: >100 bpm, Increment >15 bpm, Increment >30 bpm, <60 bpm, Decrement >15 bpm, Decrement >30 bpm Respiratory Rate: >20 breaths/min, <12 breaths/min Body temperature: >38 °C, <36 °C Office SBP (mmHg): > 160 mmHg, Increment > 40 mmHg, < 90 mmHg, Decrement > 40 mmHg Office DBP (mmHg): > 100 mmHg, Increment > 20 mmHg, < 50 mmHg, Decrement > 20 mmHg
Definition	:	
 If multiple observation occurs to the same patient, then count that patient as one patient.

12.3 ECG

12.3.1 Summary of Electrocardiogram Results by Visit

Target population	:	Safety Analysis Set
Analysis Items	:	ECG Ventricular rate, RR Interval, PR Interval, QRS Duration, QT Interval, QTcF Interval
Group	:	Placebo, Zilebesiran 300 mg, Zilebesiran 600 mg, Total zilebesiran, Overall Total
Time of analysis	:	Single 12-lead ECG: Refer to section 2.8.1 24-hour Holter ECG: Refer to section 2.8.2
Content of analysis	:	
 Calculate the summary statistics of measurement value, change from baseline and percent change from baseline for each quantitative item of the ECG test by groups and analysis time points. The baseline will be determined according to the Analysis Group The summary will be done for both Single 12-lead ECG and 24-hour Holter ECG.

12.3.2 Summary of Rhythm, Overall Interpretation of Electrocardiogram, Change from Baseline Electrocardiogram by Visit

Target population	:	Safety Analysis Set
Analysis Items	:	Rhythm, Overall Interpretation of ECG, Change from Baseline ECG
Group	:	Placebo, Zilebesiran 300 mg, Zilebesiran 600 mg, Total zilebesiran, Overall Total
Time of analysis	:	Single 12-lead ECG: Refer to section 2.8.1 24-hour Holter ECG: Refer to section 2.8.2
Content of analysis	:	
 Calculate the number of patients and the percentages by groups, analysis time points, ECG test and categories Category is as follows: Rhythm: Normal; Abnormal, not clinically significant; Abnormal, clinically significant; Not Evaluable; Missing Overall Interpretation of ECG: Normal; Abnormal, not clinically Significant; Abnormal, clinically significant; Missing Change from Baseline ECG: No significant worsening from baseline; Clinically significant worsening from baseline; Missing The summary will be done for both Single 12-lead ECG and 24-hour Holter ECG.
Definitions	:	
 The denominator of proportions is the target population by groups.

12.3.3 Shifts from Baseline to Worst Post-Baseline in QTcF Intervals on 24-hour Holter Electrocardiogram

Target population	:	Safety Analysis Set
Analysis Items	:	Worst Post-Baseline Value in QTcF Intervals, Maximum Change from Baseline in QTcF Intervals

Group	:	Placebo, Zilebesiran 300 mg, Zilebesiran 600 mg, Total zilebesiran, Overall Total
Content of analysis	:	
 • Create shift table for baseline data and post-dose visit data by analysis items and categories • Category is as follows: Worst Post-Baseline Value (msec): <=450, >450 to 480, >480 to 500, >500, Missing, Total Maximum Change from Baseline (msec): <=30, >30 to 60, >60, Missing, Total
Definitions	:	
 • If the patient performs the test but there is not assessment result data will be analyzed as “Missing” • The denominator of proportions is the target population by groups.

12.4 Laboratory Parameters

12.4.1 Summary of Laboratory Parameters by Visit

Target population	:	Safety Analysis Set
Analysis Items	:	Hematology, Serum Chemistry, Liver Function Tests, Urinalysis, Coagulation (Refer to Appendix 2)
Group	:	Placebo, Zilebesiran 300 mg, Zilebesiran 600 mg, Total zilebesiran, Overall Total
Time of analysis	:	Refer to section 2.8.1
Content of analysis	:	
 • Calculate the summary statistics of measurement value, change from baseline and percent change from baseline for each quantitative item of the laboratory test by groups and analysis time points.

Items of Clinical Laboratory Assessments

Hematology	
Complete blood count with differential	
Serum Chemistry	
Sodium	Potassium
BUN	Phosphate
Uric acid	Albumin
Total protein	Calcium
Glucose	Bicarbonate
Creatinine and eGFR ^a	Chloride
Triglycerides	
Liver Function Tests	
AST	ALP
ALT	Bilirubin (total and direct)
GGT	
Urinalysis	
Visual inspection for appearance and color	Bilirubin
pH (dipstick)	Nitrite
Specific gravity	RBCs
Ketones	Urobilinogen
Albumin	Leukocytes
Glucose	Microscopy (if clinically indicated)
Protein	
Coagulation	
Prothrombin time	International Normalized Ratio
Partial Thromboplastin Time	
Glycemic Assessment	
HbA1c	
Immunogenicity	
Anti-drug antibodies	
Pregnancy Testing/FSH Screening	
β-human chorionic gonadotropin (females of childbearing potential only)	FSH (postmenopausal women only)

Abbreviations: ALP=alkaline phosphatase; ALT=alanine aminotransferase; AST=aspartate aminotransferase; BUN=blood urea nitrogen; eGFR=estimated glomerular filtration rate; HbA1c=hemoglobin A1c; FSH=follicle-stimulating hormone; GGT=gamma glutamyl transferase; RBCs=red blood cells.

^a Refer to the Laboratory Manual for further instructions on calculating eGFR.

12.4.2 Shifts from Baseline to Worst Post-Baseline for Laboratory Parameters during 6-month DB Period

Target population	:	Safety Analysis Set
Analysis	:	Hematology, Serum Chemistry, Liver Function Tests, Urinalysis,

Items		Coagulation (Refer to Appendix 2)
Group	:	Placebo, Zilebesiran 300 mg, Zilebesiran 600 mg, Total zilebesiran, Overall Total
Time of analysis	:	Refer to section 2.8.1
Content of analysis	:	
 • Create shift table for baseline to worst post-baseline data by groups, laboratory test and grade. • Grade is as follows: Low, Normal, High, Total
Definitions	:	
 • The denominator of proportions is the target population by groups.

12.4.3 Summary of Post-Baseline Potentially Clinically Significant Abnormalities for Clinical Laboratory Data during 6-Month DB Period

Target population	:	Safety Analysis Set
Analysis Items	:	Hematology, Serum Chemistry
Group	:	Placebo, Zilebesiran 300 mg, Zilebesiran 600 mg, Total zilebesiran, Overall Total
Time of analysis	:	Refer to section 2.8.1
Content of analysis	:	
 • Calculate the number of patients and the percentages by groups, analysis items and categories • Category for Hematology is as follows Hemoglobin (g/L): <100 Lymphocytes ($\times 10^9/L$): <0.8, <0.5, >12 Neutrophils ($\times 10^9/L$): <1.5, <1.0, ≥ 12 Platelet Count ($\times 10^9/L$): <75, <50, ≥ 600 WBC Count ($\times 10^9/L$): <3.0, ≥ 16 • Category for Serum Chemistry is as follows: Albumin (g/L): <30 Calcium (mmol/L): <2.0, >2.9 Creatinine (umol/L): >2xBaseline, >3xBaseline or >4 mg/dL eGFR(mL/min/1.73m²): $\geq 30\%$ Decrease from Baseline Plasma Glucose (mmol/L): <3.0, ≥ 13.9 Serum Glucose (mmol/L): <3.0, ≥ 13.9 Phosphate (mmol/L): <0.6 Potassium (mmol/L): <3.0, >5.5, >6.0 Sodium (mmol/L): <130, >155 • Calculate for Serum Chemistry with Confirmed by repeat measure is as follows: Creatinine (umol/L): >2xBaseline, Confirmed by repeat measure eGFR(mL/min/1.73m²): $\geq 30\%$ Decrease from Baseline, Confirmed by repeat measure Potassium (mmol/L): >5.5, Confirmed by repeat measure
Definitions	:	
 • The denominator of proportions is the target population by groups. • Repeat measure: the abnormal criteria was present for consecutive (non-missing) collections.

12.4.4 Shifts from Baseline to Worst Post-Baseline in eGFR (mL/min/1.73m²) during 6-month DB Period

Target population	:	Safety Analysis Set
Analysis Items	:	eGFR (mL/min/1.73m ²)
Content of analysis	:	
 • Create shift table for baseline to Worst post-baseline data by category. • Category is as follows: >=90 (mL/min/1.73m²), 60 to <90 (mL/min/1.73m²), 45 to <60 (mL/min/1.73m²), 30 to <45 (mL/min/1.73m²), 15 to <30 (mL/min/1.73m²), <15 (mL/min/1.73m²), Missing, Total
Definition	:	• The denominator of proportions is the target population by groups.

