5.7.4. Monitoring and Approach for Potential Hyperkalemia

The Schedule of Assessments (Table 1) includes frequent laboratory monitoring of serum electrolytes (at least monthly through the anticipated onset of zilebesiran PD). The guidelines in Table 4 apply for potassium elevations detected by laboratory monitoring.[McMurray 2016; Parving 2012]

Table 4: Recommended Interventions for Hyperkalemia

Serum K ⁺ >5.2 and <5.5 mmol/L	Serum K ⁺ ≥5.5 and <6.0 mmol/L	Serum K ⁺ ≥6.0 mmol/L

 Confirm potassium concentration in a non-hemolyzed sample. Reinforce low-potassium diet and restriction of food/drinks with high potassium content. Review medical regimen (including dietary supplements and over-the-counter medications) for agents known to cause hyperkalemia^a. Consider reduction in dose or discontinuation of these agents only if clinically acceptable. Repeat K⁺ measurement within 3 to 5 days. If K⁺ remains >5.2 and <5.5 mmol/L, regularly monitor K⁺ levels to ensure stability. 	
 Confirm potassium concentration in a non-hemolyzed sample. Apply all measures outlined for serum K⁺ >5.2 and <5.5 mmol/L. Repeat K⁺ measurement after 2 to 3 days. If K⁺ persistently elevated ≥5.5 mmol/L, consider treatment with a potassium binder. 	
 Confirm potassium concentration in a non-hemolyzed sample. Urgently evaluate patient and treat hyperkalemia as clinically indicated. After urgent treatment, consider treatment with a potassium binder. Apply all measures outlined for serum K⁺ ≥5.5 and <6.0 mmol/L.

Abbreviations: NSAID=nonsteroidal anti-inflammatory drug.

^a This list is not meant to be exhaustive: potassium-sparing diuretics (eg, amiloride and triamterene), potassium supplements (eg, potassium chloride), salt substitutes, NSAIDs, cyclo-oxygenase-2 inhibitors, trimethoprim and trimethoprim-containing combination products, herbal supplements (eg, Noni juice, alfalfa [*Medicago sativa*], dandelion [*Taraxacum officinale*], horsetail [*Equisetum arvense*], nettle [*Urtica dioica*], milkweed, lily of the valley, Siberian ginseng, hawthorn berries).

Any potassium elevation >5.5 mmol/L that has been confirmed by a second measurement (serum or plasma) or that requires clinical intervention must be reported as an AE of clinical interest (Section 6.5.6.1).

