6.5.5. Clinical Laboratory Assessments

Clinical laboratory assessments are listed in [Table 6](#) and will be assessed as specified in the Schedule of Assessments ([Table 1](#)).

Clinical laboratory tests will be evaluated by a central laboratory. Specific instructions for transaminase elevations are provided in Section 5.7.5. For any other unexplained clinically relevant abnormal laboratory test occurring after study drug administration, the test should be repeated and followed up at the discretion of the Investigator until it has returned to the normal range or stabilized, and/or a diagnosis is made to adequately explain the abnormality. Additional safety laboratories and assessments as indicated by the clinical situation may be requested. While local laboratory results may be used for urgent clinical decisions, on the day of the assessments, all laboratory assessments specified in [Table 6](#) that are performed at the clinic should also be sent in parallel to the central laboratory.

Blood samples collected for RAS biomarkers should be collected in the morning and in the seated/upright position (after blood pressure measurements and before any assessments collected in the supine position). Blood samples for laboratory evaluation should be collected after the completion of blood pressure assessments.

Spot urine collections for albumin and creatinine should be obtained in the morning.

For any safety event or laboratory abnormality, additional laboratory assessments, imaging, and consultation may be performed for clinical evaluation and/or in consultation with the Medical Monitor; results may be collected and should be included in the clinical database.

Table 6: Clinical Laboratory Assessments

Hematology	
Complete blood count with differential	
Serum Chemistry	
Sodium	Potassium
BUN	Phosphate
Uric acid	Albumin
Total protein	Calcium
Glucose	Bicarbonate
Creatinine and eGFR ^a	Chloride
Triglycerides	
Liver Function Tests	
AST	ALP
ALT	Bilirubin (total and direct)
GGT	
Urinalysis	
Visual inspection for appearance and color	Bilirubin
pH (dipstick)	Nitrite
Specific gravity	RBCs
Ketones	Urobilinogen
Albumin	Leukocytes
Glucose	Microscopy (if clinically indicated)
Protein	
Coagulation	
Prothrombin time	International Normalized Ratio
Partial Thromboplastin Time	
Glycemic Assessment (see Section 6.5.5.1)	
HbA1c	
Immunogenicity (see Section 6.5.5.2)	
Anti-drug antibodies	
Pregnancy Testing/FSH Screening (see Section 6.5.5.3)	

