6.5.6. Adverse Events

6.5.6.1. Definitions

Adverse Event

According to the ICH E2A guideline Definitions and Standards for Expedited Reporting, and 21 Code of Federal Regulations 312.32, IND Safety Reporting, an AE is any untoward medical occurrence in a patient or clinical investigational subject administered a medicinal product and which does not necessarily have a causal relationship with this treatment.

Serious Adverse Event

An SAE is any untoward medical occurrence that at any dose:

- Results in death.
- Is life-threatening (an event which places the patient at immediate risk of death from the event as it occurred. It does not include an event that had it occurred in a more severe form might have caused death).
- Requires inpatient hospitalization or prolongation of existing hospitalization.
- Results in persistent or significant disability or incapacity.
- Is a congenital anomaly or birth defect.
- Is an important medical event that may not be immediately life-threatening or result in death or hospitalization but may jeopardize the patient and may require intervention to prevent one of the other outcomes listed in the definition above (eg, events include allergic bronchospasm requiring intensive treatment in an emergency room or at home, blood dyscrasias, convulsions, or the development of drug dependency or abuse).

Adverse Events of Clinical Interest

The following are considered to be AEs of clinical interest:

- ALT or AST $>3 \times$ ULN.
- Severe or serious ISRs.

An ISR is defined as a local reaction at or near the site of injection. “At or near” the injection site includes reactions at the injection site, adjacent to the injection site, or a reaction which may shift slightly away from the injection site due to gravity (eg, as may occur with swelling or hematoma). A systemic reaction which includes the injection site, eg, generalized urticaria, other distinct entities or conditions like lymphadenopathy that may be near the injection site is not considered an ISR.
- Hyperkalemia, defined as any potassium elevation >5.5 mmol/L that has been confirmed by a second measurement (serum or plasma) or that requires clinical intervention.
- Hypotension, defined as
 - clinical signs/symptoms consistent with hypotension, including but not limited to lightheadedness, dizziness, and syncope, coupled with a significantly lower SBP compared to prior visits, OR
 - any significantly lower SBP compared to prior visits that requires clinical intervention.

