3.3.1.2 Number of Events

If more than one Adverse Event occurred in a same patient (Relationship of the Adverse Event to Study drug if counting the Relationship of the Adverse Event to Study drug, Serious Adverse Event if counting the Serious Adverse Event, Adverse Event of Clinical Interest if counting Adverse Event of Clinical Interest, Adverse Event Severity if counting Adverse Event Severity), each event will be counted respectively (no summary processing performed).

3.3.2 Handling of Prior and Concomitant Medication, Prior and Concomitant Anti-hypertensive Medication

In the tabulation of prior/concomitant medications (System organ class, High level term, Preferred Term), if the same patient uses multiple medications corresponding to the same System organ class, High level term, Preferred Term code when counting the Preferred Term, High level term when counting High level term, System organ class when counting System organ class, the data will be tabulated as one drug.

3.3.3 Handling of all evaluation safety items except for Adverse Events, Prior and Concomitant Medication, Prior and Concomitant Anti-hypertensive medication

- Missing data will not be imputed.
- If outliers are excluded from the analysis, they will be specified, and the reasons for exclusion should be stated.
- For the listing and figure by patient, not only scheduled visit data but also unscheduled visit data will be used. For figures by patient based on Labs, only central labs will be presented.
- For the table and figure of summary statistics, only scheduled visit data will be used. For tables and figures of summary statistics based on Labs, only central labs will be presented.

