3.5.2 Time Windows

For tables and figures, the visit will be defined as the following:

- For actual visits on EDC except unscheduled visit, end of treatment visit, early termination visit and end of study visit, the visit will be used as it is for analysis.
- For actual visits on EDC of unscheduled visits, the data from this visit will be used to calculate baseline, worst post baseline, and maximum post baseline only. Post baseline unscheduled visits will not be considered for by-visit analysis.
- For actual visits on EDC of end of treatment visit, early termination visit and end of study visit, the analysis visit will be as the following table. The day of administration of the investigational drug is defined as “Day 1”

Analysis visit	Reference date	Time window
Day 8	Day 8	Day 5 ~ Day 11
Day 15	Day 15	Day 12 ~ Day 18
Month 1	Day 29	Day 24 ~ Day 34
Month 2	Day 57	Day 52 ~ Day 62
Month 3	Day 85	Day 78 ~ Day 92
Month 4	Day 113	Day 106 ~ Day 120
Month 5	Day 141	Day 134 ~ Day 148
Month 6	Day 169	Day 162 ~ Day 176
Month 9	Day 253	Day 239 ~ Day 267
Month 12	Day 337	Day 323 ~ Day 351

For all listings, the visit will be displayed as the visit on EDC.

4. Statistical Analysis

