4.1 Details of the Analysis Method

4.1.1 Summary Statistics

Continuous data except plasma PK parameters and pooled urine PK parameters will be summarized using descriptive statistics including number of patients, mean, standard deviation, SEM, median, minimum, and maximum.

Plasma PK concentration, urine PK concentration, Plasma PK parameters and pooled urine of PK parameters will be summarized using descriptive statistics including number of patients, number of BLQ and percentage (%), mean, standard deviation, SEM, CV(%), median, minimum, maximum, geometric mean, and geometric mean CV (%).

Categorical variables will be summarized using frequencies and percentages.

Results will be presented as the estimated value for each treatment group, Placebo, zilebesiran 300 mg, zilebesiran 600 mg, Total zilebesiran and Overall Total.

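### Under SAP 3.5.2 as written, the confirmed potassium row in SAP 12.4.3 ignores the unscheduled repeat draw and tests persistence to the next scheduled visit

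*SAP*

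**What the plan says.** SAP 12.4.3 tabulates potentially clinically significant laboratory values by arm during the 6-month double-blind (DB) period. Besides the plain counts, it has rows confirmed by repeat measurement for potassium above 5.5 mmol/L, creatinine above twice baseline, and an eGFR fall of at least 30%. The definition is: "Repeat measure: the abnormal criteria was present for consecutive (non-missing) collections". It sets no time limit and does not mention unscheduled samples.

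The general rule is in SAP 3.5.2. For unscheduled visits in tables and figures, "the data from this visit will be used to calculate baseline, worst post baseline, and maximum post baseline only". SAP 3.3.3 adds that "For the table and figure of summary statistics, only scheduled visit data will be used", whereas "For the listing and figure by patient, not only scheduled visit data but also unscheduled visit data will be used". It also limits laboratory summary tables to central-laboratory results.

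On the protocol side, section 6.5.6.1 makes potassium above 5.5 mmol/L an adverse event of clinical interest when "confirmed by a second measurement (serum or plasma") or when it requires clinical intervention. Section 5.7.4, Table 4, recommends confirming the value in a non-hemolyzed sample. For 5.5 to below 6.0 mmol/L it also recommends a repeat "measurement after 2 to 3 days". The column for 6.0 mmol/L and above carries the same measures forward.

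**The concern.** The row and the protocol share a threshold and the word confirmed, so a reader will take the row as the by-arm count of confirmed hyperkalemia. Under 3.5.2 it is something else, because the sample that does the confirming is normally an unscheduled one.

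Safety is the primary objective, and Protocol 1.3.2 names hyperkalemia as a possible risk. In Study 002, potassium exceeded 5.5 mmol/L in 17 zilebesiran patients and no placebo patients, mostly at a single time point (Protocol 1.2). If elevations are similarly brief here, checking only at the next scheduled visit could miss those that a prompt repeat would confirm.

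No other specified table fills the gap. SAP 12.1.1 has no row for events of clinical interest. The hyperkalemia events in 12.1.2 are selected by preferred term (Appendix 3), so confirmed and unconfirmed cases are mixed. Listings 13.21, 13.23 and 13.40 show individual patients without a by-arm count. Because listings include unscheduled results, listing 13.40 can show a positive repeat for a patient whom 12.4.3 treats as unconfirmed, or a normal repeat for one it treats as confirmed.

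**Working it through.** The plan states no figure to reproduce; this is a data-handling rule. The check compares the interval the row would use with the interval the protocol recommends, then sizes the population at risk.

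**Step 1. Does the rule exclude the repeat?** SAP 3.5.2 gives a closed list of three uses. Confirmation at consecutive collections is none of them, and 12.4.3 claims no exception.

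**Step 2. Intervals between scheduled chemistry samples.** Inputs are the nominal days and windows in Protocol Table 1. The nominal gap is the later day minus the earlier day. The range subtracts and adds both windows.

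| First high value at | Next scheduled sample | Nominal gap (days) | Range with windows (days) |
|---|---|---|---|
| Day 8 ±3 | Day 15 ±3 | 7 | 1 to 13 |
| Day 15 ±3 | Day 29 ±5 | 14 | 6 to 22 |
| Day 29 ±5 | Day 57 ±5 | 28 | 18 to 38 |
| Day 57 ±5 | Day 85 ±7 | 28 | 16 to 40 |
| Day 85 ±7 | Day 113 ±7 | 28 | 14 to 42 |
| Day 113 ±7 | Day 141 ±7 | 28 | 14 to 42 |
| Day 141 ±7 | Day 169 ±7 | 28 | 14 to 42 |
| Day 169 ±7 (Month 6) | none in the DB period | – | – |

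After Month 6 the next sample is Month 9, nominally 253 − 169 = 84 days later and outside the table's period. For (5 + 1)/8 = 75% of the scheduled visits, the row's check therefore comes 28 days later or never. Table 4 recommends 2 to 3 days. The 75% counts visits and does not predict the share of patients affected.

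**Step 3. Direction of the error.**
- High at a visit, high at the prompt repeat, normal at the next visit: confirmed under the protocol, not confirmed in the row.
- High at a visit, normal at the prompt repeat, high at the next visit: the repeat did not confirm the first value, but the row counts the patient as confirmed.

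**Step 4. Patients who could be affected.** Assume the Study 002 zilebesiran rate of 5.6% applies to the 24 zilebesiran patients:
- expected number above 5.5 mmol/L = 24 × 0.056 = 1.34;
- chance of at least one = 1 − (1 − 0.056)^24 = 0.75.

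Each patient moved into or out of the row changes a 12-patient arm by 1/12 = 8.3 percentage points.

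**Step 5. Number misclassified.** This depends on how long elevations last and how often they recur. No document gives either, so no figure is offered.

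**The case against.** The strongest reply is that 12.4.3 is a specific definition and speaks of repeat measures and collections, not visits. The table is not laid out by visit, so a programmer could reasonably include unscheduled draws. That reading is available. It needs an exception that 3.5.2 does not contain, and two programmers could produce different counts.

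A reader might infer that SAP 3.3.3 and the reference to 2.8.1 independently exclude unscheduled draws. The documents do not clearly support this. Under the 4.1.1 heading on summary statistics, "Categorical variables will be summarized using frequencies and percentages" might seem to bring count tables under 3.3.3, but SAP 6.1 and 6.4 treat summary statistics and patient counts as different things. Sections 12.4.2 and 12.4.9 also cite 2.8.1, yet unscheduled data are admitted there by 3.5.2 and 3.3.3 respectively. The point rests on 3.5.2.

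A reader might also infer that the protocol defines confirmation as a repeat at 2 to 3 days. It does not: the definition in 6.5.6.1 has no interval, Table 4 is a set of recommendations, and its non-hemolyzed confirmation step is listed separately and untimed. What stands is that a draw made to check a high value would normally fall between scheduled visits.

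Finally, 12.4.3 is a laboratory table and does not claim to implement the clinical-interest definition, which investigators report on a dedicated eCRF. The unconfirmed rows above 5.5 and 6.0 mmol/L do not depend on confirmation, hyperkalemia events are tabulated by arm, and the analysis is descriptive. All of this limits the consequence. It does not make the confirmed row count what its label suggests.

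**Conclusion.** The concern holds as a should-fix point of small consequence. Followed as written, SAP 3.5.2 makes the confirmed potassium row in 12.4.3 a test of persistence to the next scheduled visit, with errors possible in both directions and no confirmation possible in the DB period for a first elevation at Month 6. The creatinine and eGFR rows share the defect. For eGFR it matters less, because the renal event of clinical interest requires no confirmation.

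About 1.3 of 24 zilebesiran patients are expected above 5.5 mmol/L, assuming the Study 002 rate carries over to this population. The number wrongly classified among them cannot be derived. A reader might infer that most confirmed cases will be lost, or that hyperkalemia will go unreported. The documents support neither: episode duration is unknown, and individual cases stay visible in the listings and adverse event tables. The primary adverse event count and the efficacy results are unaffected.

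**What to change.** In SAP 12.4.3, define a confirmed abnormality as one where the criterion is met at a post-baseline collection and again at the next non-missing central-laboratory collection, scheduled or unscheduled, including a repeat of a Month 6 value drawn after that visit. Add this use to the permitted uses of unscheduled data in 3.5.2, with a matching note in 3.3.3 for clarity. Both errors are then removed for centrally tested repeats, because a normal repeat between two high visits breaks the sequence.

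The central-laboratory restriction can stay: Protocol 6.5.5 says that listed laboratory assessments performed at the clinic "should also be sent in parallel to the central laboratory". The revised row would still omit the requires-intervention limb of the clinical-interest definition. If a count on that definition is wanted, a by-arm row of investigator-reported hyperkalemia of clinical interest could be added.

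The cost is one definition sentence, one addition to 3.5.2 and one note in 3.3.3. No new data are needed, since unscheduled potassium results are already collected and already go into listing 13.40.
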